#### 4.7.4 Facial IGA Assessment

Facial IGA assessment will be summarized with the same method of Investigator's Global Assessment (IGA).

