8 STUDY POPULATION

8.1 Inclusion Criteria

Patients must meet the following criteria for study entry:

- 1) In the opinion of the Investigator, the patient is capable of understanding and complying with protocol requirements.
- 2) The patient signs and dates a written ICF prior to the initiation of any study procedures.
- 3) The patient has a diagnosis of AD (according to the criteria established by Hanifin and Rajka, 1980). The diagnosis of AD must have been present for at least 6 months.
- 4) The patient is aged 18 to 65 years, inclusive at the time of consent. Patients of any gender are eligible.
- 5) A female patient weighs at least 45 kg and a male patient weighs at least 50 kg. The patient has a BMI between 18.0 and 32.0 kg/m² inclusive at Screening.
- 6) The EASI is \geq 12 at Screening and on Day 1.
- 7) The score on the IGA is ≥ 3 (scale of 0 to 4) at Screening and on Day 1.
- 8) The total body surface area (BSA) affected by AD is $\geq 10\%$ as assessed by the physical examination at Screening and on Day 1.
- 9) The patient has:
 - (a) not received prior treatment with topical or systemic medications OR
 - (b) the patient has active disease despite topical or systemic treatment as per the Investigator at the time of screening.
 - Prescription moisturizers or moisturizers containing additives such as ceramide, hyaluronic acid, urea, or filaggrin degradation products can be allowed if the patient agrees to continue using at the current dose during the study.
- 10) A male patient who is non-sterilized and sexually active with a female partner of childbearing potential agrees to use highly effective contraception from the time of signing the ICF throughout the duration of the study treatment and for 90 days (~5 half-lives) after the last dose of study drug (See Section 8.3).
- 11) A female patient of childbearing potential who is sexually active with a non-sterilized male partner agrees to use highly effective contraception from the time of signing the ICF throughout the duration of the study treatment and for 90 days after the last dose of study drug (See Section 8.3).
- 12) The patient has a negative urine/blood result for drugs of abuse (if there are concerns in the opinion of the Investigators regarding the use of illicit drugs, including cannabinoid products).

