# 4. Statistical Analysis

# 4.1 General Considerations for Statistical Analysis

#### 4.1.1 General Rules

No statistical hypothesis testing or inferential analyses are planned. The general analytical approach for all endpoints will be descriptive in nature.

Continuous variables (such as age) will be summarized with the observed number, mean, median, standard deviation, minimum, and maximum; categorical variables will be summarized with frequency and percentage of each category.

Unless otherwise specified, in summary tables of continuous variables, the minimum and maximum values will be displayed to the same number of decimal places as the raw data; the mean, median, and percentiles will be presented to 1 extra decimal place compared to the raw data; and the standard deviation will be displayed to 2 extra decimal places compared to the raw data. The maximum number of decimal places is 3

and values will be truncated to 3 decimal places in situations where there are more than 3 decimal places. Frequency tabulations will be presented by number and percentage, where the percentage is presented in parenthesis to 1 decimal place.

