#### 4.4.5 Baseline Disease Characteristics

Duration of AD disease and baseline atopic dermatitis severity will be summarized descriptively.

Duration of AD disease (months) = (date of first dose - date of first diagnosis + 1)/30.4375, rounded to the one decimal place.

Baseline Eczema Area and Severity Index (EASI) score will be summarized descriptively.

Baseline Global Assessment of Disease Severity (IGA) score will be tabulated, and the subject number and percentage for the score will be presented.

Baseline Peak Pruritus Numerical Rating Scale (PP-NRS) score will be summarized descriptively. The baseline PP-NRS score is based on the average of daily PP-NRS

scores for the 7 days immediately preceding Day 1. In order to calculate an average for the score, the subject must have completed the diary for a minimum of 4 days during the previous 7 days.

Baseline conjunctivitis assessment is defined as the assessment on Day 1. The percentage of subjects with/without conjunctivitis at baseline will be tabulated.

Baseline total Body Surface Area (BSA) affected by AD will be summarized descriptively.

Baseline disease characteristics will be listed by subject number.

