# 4.7.2 Investigator's Global Assessment of Disease Severity (IGA)

The IGA requires the investigator to rate the severity of AD on a scale from 0 (clear) to 4 (severe).

The baseline for IGA is defined as the score measured on Day 1.

Proportion of subjects achieving an IGA response (IGA = 0 [clear] or IGA = 1 [almost clear] on a scale of 0–4, where 4 represents severe atopic dermatitis) at 2 weeks after last dose at Week 24 with observed data will be presented. If the subject has missing value for IGA at scheduled visit, the subject will be excluded from the calculation of proportion at specify visit. The corresponding 95% two-sided confidence intervals (CI), calculated using the exact binomial distribution, will also be presented.

A listing of all IGA result will be provided by subject number.

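### Facial IGA 0/1 at Week 26 can count patients whose face was already clear or almost clear on Day 1, because the global IGA method is reused without a baseline condition

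*SAP*

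**What the plan says.** SAP section 4.7.4 is one sentence: "Facial IGA assessment will be summarized with the same method of Investigator's Global Assessment (IGA". The method it points to, in SAP section 4.7.2, is "Proportion of subjects achieving an IGA response (IGA = 0 [clear] or IGA = 1 [almost clear"), taken two weeks after the Week 24 dose, with a two-sided exact binomial 95% interval. The only rule on the denominator is "If the subject has missing value for IGA at scheduled visit, the subject will be excluded from the calculation of proportion at specify visit". Section 4.7.2 also promises that "A listing of all IGA result will be provided by subject number".

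On entry, Protocol section 8.1 states "The score on the IGA is ≥ 3 (scale of 0 to 4) at Screening and on Day 1". The other severity criteria there are EASI of at least 12 and total affected BSA of at least 10%. None refers to the face.

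The facial endpoint is exploratory (Protocol Table 5 and section 7.9.3; SAP Table 1) and is worded as the proportion at 0/1 at Week 26, again without a baseline condition.

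On baseline tables, SAP section 4.4.5 opens with "Duration of AD disease and baseline atopic dermatitis severity will be summarized descriptively". Among the items it then names is "Baseline Global Assessment of Disease Severity (IGA) score will be tabulated"; facial IGA is not named.

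**The concern.** An absolute threshold works as a response criterion only if nobody meets it at the start. Entry guarantees that for the global IGA: an eligible patient who reaches 0 or 1 has fallen by at least two grades. The guarantee does not carry over to the face. A patient can qualify on trunk and limb disease with a clear or almost clear face, remain so, and be counted as achieving facial IGA 0/1 without any change. A patient who starts at 0/1 and worsens to 2 or more stays in the denominator as not achieving it.

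If any such patients are enrolled, the reported figure combines staying clear with improving and cannot be read as a facial response rate. EASI50, EASI75 and EASI90 are reductions from baseline, so among the efficacy responder endpoints only this one can be met with no improvement. Protocol section 5.4 says the findings will be used to design a Phase 2b study, so a misread facial figure could be carried forward.

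**Working it through.** **Plan's own figure.** The documents state no figure for facial IGA. The only precision figure is for EASI75: one-sided widths of 21% (N = 20) and 19% (N = 24). The maximum distance from the estimate to the exact one-sided 95% bound is 20.8% and 18.8%, so both reproduce. They are not affected by this point.

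**Following the rule through.**
- Response: a score of 0 or 1 at the visit, with no improvement required (SAP 4.7.2, applied by 4.7.4).
- Denominator: efficacy analysis set, meaning dosed patients with any efficacy assessment after baseline (SAP section 3), less those with a missing value at the visit.
- Starting level: global IGA at least 3 for everyone; facial IGA unrestricted (Protocol 8.1 and 8.2).
- Day 1 facial score: collected (Protocol Synopsis, Efficacy Assessments; Table 1).

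Nothing in this chain removes or separates a patient who starts at facial 0/1.

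**Size.** Three quantities are needed, and the documents give none of them:
- f = share at facial 0/1 on Day 1
- k = share of those still at 0/1 at Week 26
- r = proportion reaching 0/1 among those starting at 2 or more

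Reported proportion = f·k + (1 − f)·r. Proportion among patients with facial disease = r. Difference = f·(k − r).

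Taking r = 30% as an assumption:
- f = 0: difference 0
- f = 5%: 0.05 × (0.5 − 0.3) = 1.0 point at k = 0.5; 0.05 × (1 − 0.3) = 3.5 points at k = 1
- f = 20%: 0.20 × 0.2 = 4.0 points at k = 0.5; 0.20 × 0.7 = 14.0 points at k = 1
- k = 0.30: difference 0 for any f; k below r makes it negative

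**One reported result, several meanings.** Suppose the table shows 9/20 = 45.0%, with all 20 patients observed at Week 26:

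| At 0/1 on Day 1 | Of those, still 0/1 | Among patients starting at 2 or more | Reported minus this |
|---|---|---|---|
| 0 | – | 9/20 = 45.0% | 0 |
| 1 | 1 | 8/19 = 42.1% | +2.9 points |
| 4 | 2 | 7/16 = 43.8% | +1.25 points |
| 4 | 4 | 5/16 = 31.3% | +13.75 points |
| 4 | 1 | 8/16 = 50.0% | −5.0 points |

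Each difference agrees with f·(k − r); for the fourth row, 0.20 × (1 − 0.3125) = 0.1375. The planned summary would look the same in all five cases.

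**The case against.** The SAP implements the protocol endpoint exactly. That endpoint is a status at a visit, and preferring response among affected patients is a choice of a different quantity. This stands: there is no conflict between the documents, and the protocol-defined figure should remain.

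Nothing shows that the situation will arise. No facial distribution is given, and every value of f, k and r above is assumed. Even the direction is open. This also stands, so the ranges must not be read as expected bias. The certainty attaches to the logic of the rule and not to any effect.

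Much can be recovered anyway. The by-subject listing lets a reader rebuild the subset by hand in a trial of 20 to 24 patients. The opening line of SAP 4.4.5 could be taken to cover facial severity, and SAP section 1 allows further exploratory analyses. This limits the harm, but no planned summary separates the two groups. A subset chosen after the data are seen is also weaker than one fixed beforehand.

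Restricting to facial IGA of 2 or more does not restore the two-grade fall that global entry guarantees, since 2 to 1 would count. That is true, and it is why a shift table belongs beside the subset figure.

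Little depends on the result: the endpoint is exploratory, the trial is single-arm and unblinded, and the SAP states "No statistical hypothesis testing or inferential analyses are planned". The assumed differences of 1 to 14 points are small against an exact interval of about 45 points at 9/20. This settles the priority as low. It does not make the rule suitable for the face.

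**Conclusion.** The concern holds as a conditional statement. As written, any patient at facial IGA 0/1 on Day 1 and still there at Week 26 counts as achieving the endpoint, and no entry criterion, analysis set or denominator rule prevents it. Whether the Day 1 facial distribution will be tabulated is unclear. The size cannot be found from the documents: it is zero if every patient starts at facial IGA 2 or more, and otherwise f·(k − r), which may be positive or negative. The primary endpoint and sample size are not affected. This is an optional improvement.

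**What to change.** In SAP section 4.7.4, keep the all-patient facial IGA 0/1 proportion as the protocol defines it. Beside it, specify the proportion with its exact two-sided 95% interval among patients with facial IGA of at least 2 on Day 1, state that denominator, and name this as the figure to be read as response. The cut at 2 is simply the complement of 0/1: these are the patients for whom reaching 0/1 is a change. Add a Day 1 to Week 26 facial IGA shift table for the efficacy analysis set, which gives the baseline distribution and shows how many changes are a single grade. Note that the subset figure is still uncontrolled and does not estimate a treatment effect.

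The cost is one or two sentences and one table, with no new data and no change to the protocol endpoint. The drawback is a second facial figure with a smaller denominator and a wider interval. With 4 of 20 patients at 0/1 on Day 1, the exact 95% interval is 47.6 points wide for 5/16, 50.4 for 7/16 and 50.7 for 8/16, against 45.4 for 9/20 (23.1% to 68.5%).

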#### 4.8 Safety Analysis

The safety analysis will be summarized in safety analysis set.

#### 4.8.1 Drug Exposure and Compliance Analysis

Below parameters will be presented for BSI-045B:

- Number of injections received
- Duration of exposure (weeks)
- Total protocol-planned dose (mg)
- Total administered dose (mg)
- Actual dose intensity (mg/week) for loading dose
- Actual dose intensity (mg/week) for maintenance dose
- Relative dose intensity (%)
- Number of subjects with dose missed and reason for dose missed
- Number of subjects with dose changed and reason for dose changed
- Number of subjects with injection interrupted and reason for injection interrupted

Duration of exposure (weeks) = (Date of last study drug injection – date of first study drug injection + 14 days) / 7.

Total protocol-planned dose (mg) for BSI-045B =  $300 \text{ mg QW} \times 4 \text{ times} + 300 \text{mg}$  Q2W×10 times = 4200 mg

Version: V1.0

Total administered dose (mg) = Sum of doses administered for both loading dose and maintenance dose.

Actual dose intensity (mg/week) for loading dose = Sum of doses administered (mg) duration of exposure (weeks) in loading dose period.

Actual dose intensity (mg/week) for maintenance dose = Sum of doses administered (mg) /duration of exposure (weeks) in maintenance dose period.

Relative dose intensity (%) for BSI-045B = Total administered dose (mg) / Total protocol-planned dose (mg)\*100%.

In addition, the Relative dose intensity (%) for BSI-045B will be categorized to the groups: <50%, 50% to <70%, 70% to <90%, 90% to <110%, >=110%.

#### 4.8.2 Adverse Events

Adverse events will be coded using the MedDRA dictionary version 27.0 or higher. The severity of the toxicities will be graded according to the NCI CTCAE version 5.0.

Treatment emergent adverse events (TEAEs) are defined as AEs that started or worsened in severity on or after the first dose of study drug.

TEAEs will be summarized by system organ class (SOC) and preferred term (PT) in descending order of frequency. For each TEAE, the percentage of participants who experience at least 1 occurrence of given event will be summarized.

Causal relationship and toxicity grade are required entries on the adverse events eCRF, so missing data are not expected. However, any AEs with missing causal relationships will be imputed as 'Related' and any missing toxicity grades will be imputed to grade 3 for summary but still keep missing in listing.

A subject with more than one occurrence of the same adverse event in a particular system organ class will be counted only once in the total of those experiencing adverse events in that particular system organ class. If a subject experience the same adverse event at more than one severity, or with more than one relationship to study drug, the most severe rating or the stronger causal relationship to study drug will be given precedence.

The numbers of subjects and incidence rate for all TEAEs, TEAEs of BSI-045B-related for following category will be tabulated:

- 1) Overview of TEAEs
- 2) TEAEs by SOC and PT
- 3) TEAEs by SOC and PT and by Maximum NCI CTCAE grade
- 4) Serious TEAEs by SOC and PT
- 5) Grade>=3 TEAEs by SOC and PT
- TEAEs Leading to BSI-045B Interruption by SOC and PT

7) TEAEs Leading to BSI-045B Withdrawn by SOC and PT

8) TEAEs Leading to Death by SOC and PT

The following AE listings of all subjects will be provided.

- 1) All AEs
- 2) BSI-045B Related AEs
- 3) Serious AEs
- 4) AEs Leading to BSI-045B Withdrawn
- 5) AEs Leading to Death

#### 4.8.3 Clinical laboratory Tests

Clinical laboratory tests include hematology, chemistry, coagulation and urinalysis.

Laboratory parameters with numeric value and their change from baseline will be summarized descriptively on scheduled visit, minimum post-baseline value and maximum post-baseline value.

A listing of clinically significant abnormal values (including all abnormal values at scheduled visits and unscheduled visits) will be provided by subject number.

Urine and blood pregnancy test results will be listed only by subject number.

#### 4.8.4 Vital Signs

For parameters of vital signs, measured values and changes from baseline will be summarized descriptively on scheduled time point, minimum post-baseline value and maximum post-baseline value.

A listing for all parameter values of vital signs, and for marked abnormal values will be provided by subject number.

#### 4.8.512-Lead ECG

For parameters of 12-lead ECG, measured values and changes from baseline will be summarized descriptively on scheduled time point, minimum post-baseline value and maximum post-baseline value.

ECG interpretation will be summarized with shift table from baseline to post-baseline timepoint and from baseline to worst post-baseline assessment with respect to clinical classification (Normal, Abnormal, NCS, Abnormal, CS).

Refer to the following definitions for summary of abnormal QTcF intervals:

Absolute values of QTcF intervals will be classified as:

- >450 msec to <=480 msec
- >480 msec to <=500 msec

• >500 msec

Changes of QTcF intervals from baseline will be classified as:

- Prolongation <= 30 msec
- Prolongation > 30 msec to <= 60 msec
- Prolongation > 60 msec

A listing of all ECG parameter will be provided by subject number.

#### 4.8.6 Physical Examination

Physical examination results will not be summarized. A listing of all physical examination results will be provided by subject number.

#### 4.8.7 Injection Site Reaction Assessment

The number, incidence of subjects with any injection site reaction will be summarized through the study. The incidence of each type (Pain, Tenderness, Erythema/Redness, and Induration/Swelling) and it's severity of injection site reaction will also be tabulated.

A listing of injection site reaction assessment will be provided by subject number.

# 4.8.8 Hospitalization Information

Hospitalization information will not be summarized. A listing of all hospitalization information will be provided by subject number.

# 4.8.9 Conjunctivitis Assessment

Treatment-emergent conjunctivitis is defined as conjunctivitis that started or worsened in severity on or after the first dose of study drug.

Treatment-emergent conjunctivitis will be summarized by worst post-baseline severity score.

A listing of conjunctivitis assessment will be provided by subject number.

#### 4.9 Immunogenicity Analysis

The titers of anti-drug antibodies (ADA)-positive subjects will be listed, and the number, incidence of subjects with treatment emergent ADA after administration of BSI-045B will be described by blood sampling time points. The time to onset, titer, and duration of the presence of ADAs will be described using the mean, SD, median, quartiles, minimum, and maximum.

A listing of immunogenicity assessment will be provided by subject number.

#### 4.10 Pharmacokinetics Analysis

For BLQ (below the lower limit of quantification) data before first dose, it will be analyzed as "0". Concentrations of BSI-045B in serum will be summarized by time

A listing of pharmacokinetics assessment will be provided by subject number.

Other detailed PK analyses, including the derivation of PK parameters, will be provided in the PK Analysis Plan.

#### 4.11 Pharmacodynamics/biomarker Analysis

point using descriptive statistics.

For all pharmacodynamic/biomarkers evaluated in the present study, including serum levels of CCL17, periostin, total serum IgE, and perioheral eosinophil count will be statistically analyzed. The baseline for pharmacodynamics/biomarker parameter is defined as the last non-missing measured value prior to or on Day 1.

For BLQ (below the lower limit of quantification) data, it will be analyzed as "1/2 LLOQ". For > ULOQ data, it will be analyzed as "ULOQ". For all parameters, raw data, absolute and percent changes from baseline will be summarized by time point using descriptive statistics.

Mean (± standard deviation) of percent change from baseline will be plotted at scheduled visit.

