11.8 Pharmacodynamic Biomarker Analysis

The biomarker levels of patients (values and percent changes from baseline) will be summarized by descriptive statistics.

V4.0_8 Jul 2024 Page 63 of 68

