# 4.1.2 Baseline Definition and Change from Baseline and Percent Change from Baseline

Baseline data are defined as last non-missing assessment which are collected prior to or on the day of first dose, and must be prior to the administration of first dose, including scheduled and unscheduled visits, unless otherwise specified. Hence, change from baseline = post-baseline value – baseline value. Percent change from baseline = (post-baseline value – baseline value)/ baseline value×100%.

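### SAP 4.11 caps biomarker results at the ULOQ before computing change, so a patient above it at baseline and follow-up is recorded as exactly 0% change, and a fall from a baseline above it is understated

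*SAP*

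**What the plan says.** SAP 4.11 names four markers: CCL17 (TARC), periostin, total IgE and eosinophil count. Its substitution rules apply to all of them. Results below the lower limit become half that limit. For results above the upper limit the text is "For > ULOQ data, it will be analyzed as" the ULOQ. There is no exception for baseline, which is taken from the same measurements: "The baseline for pharmacodynamics/biomarker parameter is defined as the last non-missing measured value prior to or on Day 1".

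The substituted data then feed every planned summary: "For all parameters, raw data, absolute and percent changes from baseline will be summarized by time point using descriptive statistics". Mean percent change with SD is also plotted by visit. SAP 4.1.2 gives the usual formula, the difference from baseline divided by baseline. Protocol 11.8 is consistent with this: "The biomarker levels of patients (values and percent changes from baseline) will be summarized by descriptive statistics".

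SAP 4.11 plans no count or flag of values at the ceiling, no sensitivity summary and no by-subject biomarker listing, although SAP 4.9 and 4.10 plan listings for immunogenicity and PK. Neither document states a ULOQ or says whether over-range samples are diluted and re-assayed. Protocol 7.9.1 describes commercial kits and leaves assay detail to the laboratory manual.

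**The concern.** A result above the ULOQ says only that the true value is at least that high. Using the ULOQ as if it were measured does limited harm to a table of raw values. It does more harm to a change from baseline, because the capped value can enter both the numerator and the denominator. For a marker that treatment lowers, levels are highest before treatment, so the cap falls mainly on baselines, and on the patients with the highest levels.

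The trial is single-arm with 20 to 24 evaluable patients (Protocol 7.1), so a few capped baselines can move a summary and no control group shows the same compression. Protocol 5.5 argues that higher doses may strengthen the biomarker response, and Protocol 5.4 says the findings will be used to design Phase 2b. A muted fall would blur that reading. Without a flag or listing, a reader of the report could not tell a true 0% from one created by the rule.

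**Working it through.** The plan gives no figure for this point. Its only precision calculation concerns EASI75 and plays no part here.

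**Step 1. One patient.** Inputs are the percent-change formula in SAP 4.1.2 and the cap in SAP 4.11. Write values as multiples of the ULOQ, so the capped value is min(value, 1).

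| Baseline → follow-up | True change | Recorded under SAP 4.11 |
|---|---|---|
| 3 → 2 | (2 − 3)/3 = −33.3% | (1 − 1)/1 = 0% |
| 5 → 1.1 | (1.1 − 5)/5 = −78.0% | (1 − 1)/1 = 0% |
| 2 → 0.5 | (0.5 − 2)/2 = −75% | (0.5 − 1)/1 = −50% |
| 0.8 → 1.6 | (1.6 − 0.8)/0.8 = +100% | (1 − 0.8)/0.8 = +25% |
| 0.8 → 0.4 | −50% | −50% |

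Within a patient, the cap can only move the recorded change toward zero.

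**Step 2. Group mean, simple case.** Suppose every patient truly changes by the same percentage and k of 20 are above the ULOQ at both times. The reported mean is the true mean × (1 − k/20). For a true −50%:
- k = 1: −50 × 0.95 = −47.5%
- k = 2: −50 × 0.90 = −45%
- k = 4: −50 × 0.80 = −40%
- k = 8: −50 × 0.60 = −30%

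**Step 3. Group mean, with baselines spread around the ceiling.** These inputs are assumptions; none is in the documents:
- baseline/ULOQ is log-normal with log-SD 1.0 or 1.5, placed so that a share p of baselines exceeds 1;
- follow-up = baseline × (1 − fall) × log-normal noise with mean 1 and log-SD 0.3;
- the true percent change does not depend on baseline.

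Both values are capped at 1 and the percent change is averaged. For a true mean fall of 50%:

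| Share of baselines above ULOQ | Reported mean fall (log-SD 1.0 to 1.5) |
|---|---|
| 0% | 50% |
| 5% | about 49% |
| 10% | 47–48% |
| 20% | 44–45% |
| 50% | 31–34% |

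For a true mean fall of 30% at log-SD 1.5, the reported fall is 28%, 26% and 18% with 10%, 20% and 50% above.

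The median is affected too, but less at moderate shares. With 20% above, log-SD 1.0 and a true mean fall of 50%, it moves from −52.2% to −49.2%. Leaving out patients whose baseline is above the ULOQ recovers −50% in this model, because the assumed effect does not vary with baseline.

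**Step 4. Does the group mean always move toward zero?** No. Take 16 uncapped patients at −30% and 4 patients above the ULOQ at both times who truly rose by 50%. The true mean is (16 × −30 + 4 × 50)/20 = −14%. The reported mean is (16 × −30 + 4 × 0)/20 = −24%. The toward-zero direction at group level assumes that the capped patients fell.

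**The case against.** The strongest objection is that the rule may hardly ever be used. It matters only for results finally reported as above the ULOQ. If the laboratory dilutes and re-assays over-range samples, the cap is a rare fallback with little or no effect. The laboratory manual would settle this, and it is not among the documents. This limits what can be said about size. It does not rescue the rule, which gives a wrong change whenever it is applied.

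Second, the effect is small at low shares. With 10% of baselines above the ULOQ the shift is 2 to 3 points, below the standard error of the mean at n = 20 in the same model (about 3.4 points). That is fair, although a bias, unlike sampling error, does not average out.

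Third, for a marker that falls the error is conservative: it cannot create a fall in an individual patient. That also stands, with the group-level exception in Step 4.

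Fourth, the stakes are modest. The biomarkers are exploratory in Protocol Table 5 and SAP Table 1 (the protocol synopsis lists them among the secondary endpoints). SAP 4.1.1 plans no hypothesis tests, and no decision threshold uses a biomarker.

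A reader might go further and infer that IgE and TARC are the markers being masked. The documents do not support this. One rule covers all the markers, and no ULOQ or baseline level is given for any of them.

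A reader might also conclude that no change should ever be computed from a substituted baseline. That goes too far. A baseline above the ULOQ with a quantifiable follow-up gives a valid minimum fall, and a blanket ban would also exclude baselines set to half the LLOQ.

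**Conclusion.** The point holds as a defect in a stated rule. From SAP 4.1.2 and 4.11 alone, a patient above the ULOQ at both times gets exactly 0%, and a patient above it only at baseline gets an understated fall. If the drug lowers the marker, mean and median falls are biased toward zero.

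The size cannot be fixed from the documents. Under the Step 3 assumptions, a true mean fall of 50% loses about 1 point when 5% of baselines are above the ULOQ, 5 to 6 points at 20%, and 16 to 19 points at 50%. It loses nothing if over-range samples are diluted and re-assayed. A claim that the bias is large in this trial, or that it falls on a particular marker, would go beyond the evidence. The consequence is confined to exploratory, descriptive biomarker results; EASI75 and safety are untouched. The change is worth making because it is cheap and the artefact would otherwise be invisible in the report.

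**What to change.** Amend SAP 4.11 as follows:

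- Keep ULOQ substitution for raw-value summaries only.
- When baseline and follow-up are both above the ULOQ, report change and percent change as not estimable, not as 0%.
- When only baseline is above the ULOQ, flag the computed value as a minimum fall.
- Report the number of results above the ULOQ by marker and visit.
- Add a by-subject biomarker listing that shows the flags.
- Add a sensitivity summary that either excludes patients whose baseline is above the ULOQ or uses a censored-data method.
- Where the laboratory already obtains a diluted re-assay result, state that the measured value is used.

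The fix should not depend on new re-assays, because neither document provides for retained biomarker samples.

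The cost is SAP wording and a few added outputs, with no extra visit or blood draw. The downside is that a few patients may lack a percent change for one marker. Excluding patients with a high baseline can itself shift the result if the effect depends on baseline, which is why the exclusion belongs in a sensitivity summary.
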